11.2.3 Contingency Plan For Insufficient Primary Endpoint Events

The projected event rate of 60% at 4 years for the primary composite endpoint in CON participants was based on multiple data sources. Although we believe the projected rate is reasonably conservative, an acceptably precise estimate of the true event rate of the primary endpoint will not be known until substantial participant recruitment and follow-up have been accrued. To ensure that the primary analysis is well-powered and useful, a prospective plan to allow extending follow-up and/or changing the primary endpoint based on aggregate event rate data will be established prior to the first review of unblinded trial data. At a designated time during the trial, an analysis will be conducted to estimate the overall aggregate primary endpoint event rate and project the final number of observed events. If the estimated unconditional power (i.e. based on aggregate event rate data; not by treatment group) is less than the originally targeted 90%, then one or more of the following options will be considered:

1. Extend follow-up to allow more events to accrue.
2. Change the primary endpoint to one that occurs more frequently.
 - The current primary endpoint would become a secondary endpoint
 - The proposed new primary endpoint would be the composite of death, MI, resuscitated cardiac arrest, or hospitalization for unstable angina or heart failure.
3. Follow the recommendation of an independent advisory panel.

An independent advisory panel, separate from the DSMB, will be convened for the purpose of reviewing unconditional power estimates and making a recommendation to the NHLBI Director. Members of this panel will not have access to unblinded data by treatment group or other data that may bias their recommendation.^{33, 34} Additional details will be finalized in cooperation with the DSMB and recorded in the statistical analysis plan before the first unblinded interim analysis.

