Data and Safety Monitoring Board	An independent Data and Safety Monitoring Board will advise the NHLBI and study leadership on safety aspects and overall progress of the study.
Statistical Considerations	A sample size of approximately 1,000 randomized participants is expected to provide ≥80-95% power to detect a 15%-19% reduction in the primary composite event rate in participants randomized to INV as compared with CON strategy.

TABLE OF CONTENTS

1.	LIST OF ABBREVIATIONS AND DEFINITIONS.....	11
2.	BACKGROUND AND RATIONALE.....	15
3.	STUDY OBJECTIVES	16
4.	STUDY DESIGN.....	17
4.1	Study Flow	17
4.2	Study Population.....	19
4.3	Inclusion/Exclusion Criteria	19
4.3.1	Criteria Prior to Informed Consent	19
4.3.2	Criteria After Enrollment (Informed Consent) and Prior to Randomization	20
5.	STUDY PROCEDURES	21
5.1	Qualifying Ischemia Test.....	21
5.2	Informed Consent Process	21
5.3	Interactive Voice Response System (IVRS) and Interactive Web Response System (IXRS).....	21
5.4	Core Lab Ischemia Verification.....	22
6.	MANAGEMENT STRATEGIES	23
6.1	Conservative (CON) Strategy.....	23
6.2	Invasive (INV) Strategy	23
6.3	Optimal Medical Therapy (OMT).....	23
6.3.1	Management of Angina in CON Participants.....	24
6.3.2	Management of Angina in INV Participants	24
6.4	Optimal Revascularization Therapy (ORT)	24
6.4.1	Criteria to Select PCI vs. CABG	25
6.4.2	Guidelines for Optimal Percutaneous Coronary Intervention.....	25
6.4.3	Guidelines for Optimal Surgical Revascularization	25
6.5	Maximizing Adherence to CON Strategy.....	25
6.6	Cath in Participants Randomized to CON Strategy	26
7.	AUXILLIARY SCREENING LOG	28
7.1	Screening Log.....	28
8.	Study Assessments	29
8.1	Creatinine and Pregnancy Test.....	29
8.2	Standard Blood Tests.....	29
8.3	Endpoint Assessments.....	29

8.4	Blood Biomarkers and Genomics Biorepository	29
8.5	Medication Adherence	30
8.6	Lifestyle Assessment	30
8.7	Quality of Life Assessment.....	30
8.8	Economics Assessment.....	30
9.	SCHEDULE OF ASSESSMENTS	31
10.	ADJUDICATION OF CLINICAL EVENTS	40
11.	STATISTICAL CONSIDERATIONS AND ANALYSIS PLAN	41
11.1	Sample Size Determination and Statistical Power	41
11.1.1	Summary of Power and Precision	41
11.2	Statistical Analysis Plan	41
11.2.1	Analysis of the Primary Endpoint	42
11.2.2	Analysis of the Secondary Endpoints	42
11.2.3	Contingency Plan For Insufficient Primary Endpoint Events	43
11.2.4	Quality of Life (QOL) Analysis.....	43
11.2.5	Health Economics Analysis	44
11.2.6	Interim Analysis	44

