4.1 Study Flow

See figure 1 for details. Patients with advanced CKD and at least moderate ischemia (see section 5.1) will be identified and screened for clinical inclusion/exclusion criteria (see section 4.3). Patients who are suspected to be trial eligible may also be pre-screened, for example, prior to clinically indicated ischemia testing in clinical areas where SIHD patients are cared for. Patients who meet clinical and ischemia (site-interpreted) eligibility criteria and are interested in participating in the trial will be enrolled by signing an informed consent and receiving a study number via the interactive voice response system (IVRS) or interactive web response system (IXRS) (see section 5.3). Ischemia test data (e.g., images, ECG, report) will be transferred to the relevant core lab electronically for enrolled participants (see Figure 1).

Participants with known or a high likelihood of unprotected left main stenosis $\geq 50\%$ will be excluded before randomization. Timing of Randomization: Participants determined to be eligible for randomization should be randomized within a target of 15 days of consent, and participants randomized to INV strategy should undergo catheterization within a target of 30 days after randomization, with optimal revascularization therapy (ORT) soon thereafter as appropriate. Participants will be enrolled over approximately 3.5 years. Randomized participants will be followed for an average of approximately 4 years. The minimum follow-up period for randomized participants will be approximately 18-24 months following randomization of the final participant. A schedule of assessments is provided in [section 9](#).

Figure 1 Study Flow

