11. STATISTICAL CONSIDERATIONS AND ANALYSIS PLAN

11.1 Sample Size Determination and Statistical Power

11.1.1 Summary of Power and Precision

As shown in Tables 3 and 4 below, the planned sample size of approximately 1,000 randomized participants will result in an estimate of the hazard ratio that differs from the true hazard ratio by no more than a factor of 1.19 with 95% probability and will yield power $\geq 80-95\%$ for comparing the primary composite endpoint across the two randomized groups assuming the 4-year cumulative rate of the primary composite endpoint is 60% in participants randomized to CON strategy and is less by a factor of 15% to 19% (relative reduction) in participants randomized to INV strategy. Power and precision under other assumptions are summarized in [Table 5](#) and [Table 6](#) below.

CON anticipated 4-year event rate	Power		
	$\Delta = 0.15$	$\Delta = 0.17$	$\Delta = 0.19$
Event %			
45%	56	67	76
50%	64	75	84
55%	73	83	90
60%	81	90	95
65%	88	95	98
70%	94	98	99

NOTE: Δ denotes relative reduction in 4-year event rate in INV vs. CON groups. **Assumptions:** Two-sided log-rank test with $\alpha = 0.05$; 500 participants per group; average follow-up 3.7 years; loss-to-follow-up 1% per year; survival times follow exponential distribution.

CON anticipated 4-year event rate	Margin of Error (MOE)		
	$\Delta = 0.15$	$\Delta = 0.17$	$\Delta = 0.19$
Event %			
45%	1.22	1.22	1.23
50%	1.21	1.21	1.21
55%	1.20	1.20	1.20
60%	1.19	1.19	1.19
65%	1.18	1.18	1.18
70%	1.17	1.18	1.18

NOTE: Margin of Error is the anti-log of the expected half-width of the 95% confidence interval for the log-hazard ratio. Assumptions: Based on a univariable Cox model with a binary treatment indicator and Wald-type 95% confidence intervals.

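### Is the contingency trigger of 90% power undefined because no effect size is attached to it?

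*Combined protocol and SAP*

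**What the plan says.** Section 11.2.3 (Contingency Plan For Insufficient Primary Endpoint Events) projects a 60% event rate at 4 years in the conservative (CON) arm. It provides for one analysis of the pooled primary event rate at a designated time. Unconditional power is to be estimated "based on aggregate event rate data; not by treatment group". The rule then reads that if this estimate "is less than the originally targeted 90%, then one or more of the following options will be considered". Three options are listed: a longer follow-up, a more frequent primary endpoint, or the advice of an independent panel. The panel is separate from the DSMB, sees no data by arm and makes a recommendation to the NHLBI Director. The section ends: "Additional details will be finalized in cooperation with the DSMB and recorded in the statistical analysis plan before the first unblinded interim analysis".

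The Synopsis says that about 1,000 participants "is expected to provide ≥80-95% power to detect a 15%-19% reduction in the primary composite event rate". The power table in Section 11.1.1 defines its effect measure as one that "denotes relative reduction in 4-year event rate in INV vs. CON groups", and assumes "average follow-up 3.7 years; loss-to-follow-up 1% per year", 500 per arm, exponential survival and a two-sided log-rank test at 0.05. Its 60% row prints 81, 90 and 95 for reductions of 15%, 17% and 19%; its 55% row prints 73, 83 and 90. Section 4.1 says: "Randomized participants will be followed for an average of approximately 4 years".

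**The concern.** A pooled event rate becomes a power figure only once an effect size is fixed. Section 11.2.3 speaks of an original 90% target, but no other section states one. Elsewhere there is a range of power for a range of reductions, and 90 is printed in two cells of the table: 60% CON with a 17% reduction, and 55% CON with 19%. The table's own rows show that the choice of column can decide the answer. With the planned 60% met exactly, the 15% column is below 90, the 17% column is at it and the 19% column is above it.

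Two further choices are not spelled out: whether the relative reduction or the hazard ratio is held when the observed rate departs from 60%, and which mean follow-up enters the projection. Because the trigger can lead to a change of primary endpoint, one would want it fixed before anyone could be suspected of choosing the assumption that gives the preferred answer.

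**Working it through.** **Inputs (Section 11.1.1).** 500 per arm; two-sided alpha 0.05; exponential survival; loss of 1% per year, so η = −ln(0.99) per year; mean follow-up T = 3.7 years. As a sensitivity range I also use T = 4 years (Section 4.1) and uniform entry over 3.5 years centred on the same mean. Uniform entry is an assumption; the enrolment period of about 3.5 years is stated.

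**Formulas.** For CON 4-year rate p and relative reduction Δ:

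- λ₀ = −ln(1 − p)/4; λ₁ = −ln(1 − p(1 − Δ))/4; HR = λ₁/λ₀
- events per arm (fixed follow-up) = 500 · λ/(λ + η) · (1 − exp(−(λ + η)T))
- power = Φ(|ln HR| · √D/2 − 1.96), where D is total events (Schoenfeld)
- aggregate 4-year rate = p(1 − Δ/2)

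**Step 1: reproduce the plan's figure.** With p = 0.60, Δ = 0.17 and T = 3.7, the INV rate is 0.60 × 0.83 = 0.498.

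- λ₀ = 0.2291, λ₁ = 0.1723, HR = 0.752
- D = 281 + 232 = 513
- power = Φ(0.2849 × 22.65/2 − 1.96) = Φ(1.27) = 89.7%, printed as 90

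The full 60% row comes out at 81.4/89.7/95.0 (printed 81/90/95) and the 55% row at 73.2/83.2/90.4 (printed 73/83/90). All 18 cells agree within 1 point, so the method is the plan's.

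**Step 2: where power equals 90%, relative reduction held.**

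| Setting | 17%: CON rate, aggregate, events | 19%: CON rate, aggregate, events |
|---|---|---|
| 3.7 y, fixed | 60.2%, 55.1%, 515 | 54.7%, 49.5%, 461 |
| 3.7 y, uniform | 60.7%, 55.6%, 509 | 55.1%, 49.9%, 456 |
| 4.0 y, fixed | 59.0%, 54.0%, 530 | 53.3%, 48.2%, 473 |
| 4.0 y, uniform | 59.4%, 54.4%, 525 | 53.7%, 48.6%, 470 |

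At an aggregate rate of 52%, for example, power is 85.1-87.5% at 17% (trigger met) and 92.4-94.0% at 19% (not met). The arithmetic behind the concern is therefore right: the effect size matters.

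**Step 3: which effect size does the text point to?** Section 11.2.3 names the 60% projection in the same paragraph as the 90%. In the table's 60% row, 15% gives 81 and 19% gives 95, so neither can be the source of a 90% target. Only 17% gives 90, and it is the midpoint of 15-19%. The other 90 (55% CON, 19%) lies off the projected rate.

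**Step 4: does holding the HR instead matter on that reading?** With HR held at 0.752, 90% power needs 4(1.960 + 1.282)²/(ln 0.752)² = 518 events in every setting. The relative-reduction crossings were 515, 509, 530 and 525, so the differences are 3, 9, 12 and 7 events. As aggregate rates, the HR-held crossings are 52.7-56.5%, against 54.0-55.6% with the reduction held. At aggregate rates of 52% and 48%, both conventions put power below 90% in all four settings, so the decision is the same. The conventions coincide at the 60% design rate and the crossing lies close to it, which is why so little turns on the choice.

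**Step 5: follow-up.** At 60% and 17%, power is 89.2-89.7% with a 3.7-year mean and 90.7-91.1% with 4 years: a spread of about 2 points around a rounded target.

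**The case for a change.** The strongest case for acting is that it would be cheap and that 60% with 17% is still an inference. Nothing in Section 11.2.3 says that the effect size will be among the details to be recorded. A 19% reading would lower the crossing by more than 50 events (515 − 461 = 54 with fixed 3.7-year follow-up). At 19% the choice between reduction and hazard ratio does bite: at an aggregate rate of 48%, power is 87.6-89.8% with the reduction held and 91.8-93.5% with HR 0.726 held. And with a 3.7-year mean the on-plan trial computes just under 90%, while with 4 years it computes just over.

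What stands is that the effect size is not written beside the 90%. The rest carries little weight. The reversal at 48% needs the 19% reading, which the 60% row does not support. A computed 89.2-89.7% against a printed 90 is a rounding-level gap, and it would matter only if the trigger were a sharp automatic rule; it opens consideration of options. Nor is there a contradiction to reconcile: 90% lies inside the range of 80-95%, and 3.7 years is approximately 4. As for the deferral, the details must be "recorded in the statistical analysis plan before the first unblinded interim analysis", and nobody could compute the power estimate without settling the effect size and follow-up first.

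**Conclusion.** The observation is accurate but calls for no change. Section 11.2.3 does not name the effect size behind its 90%, and in principle the choice moves the crossing from 509-530 events (17%) to 456-473 (19%). In practice the projected 60% rate and the power table single out a 17% relative reduction. On that reading the remaining choice of what to hold fixed is worth 3-12 events.

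The section already requires the details to be recorded before any unblinded interim look. The estimate uses pooled data only, and the panel cannot see results by arm, so an assumption could not be picked to suit an emerging treatment difference. Writing the effect size down would alter no stated number, rule or method. It is good practice when the promised details are drafted, not a defect in the design.

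This rests on exponential survival, 1% yearly loss, a mean follow-up of 3.7 to 4 years, and fixed follow-up or uniform 3.5-year entry. It also rests on the inference that the 90% is the 60%/17% cell.

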11.2.4 Quality of Life (QOL) Analysis

All QOL comparisons will adhere to the intention-to-treat principle. For each QOL measure examined in this study, data analysis will proceed in several stages. First, we will provide simple descriptive and comparative analyses by intention-to-treat. Statistical power estimates for this part of our analysis, based on data collected in the COURAGE trial, show that we should have in excess of 99% power to detect $\frac{1}{4}$ SD differences in our 3 principal QOL measures. Second, we will examine changes over time from baseline and identify the major determinants of those changes using regression analysis. Since there is currently no consensus in the statistical literature about the best way to deal with the multiple comparisons problem arising from testing each individual scale separately, we propose two complementary approaches. First, we will pre-specify the angina frequency and QOL scales from the SAQ as the CAD-specific measures of primary interest and assign all other comparisons to a secondary (descriptive) status. Second, we will employ a mixed model methodology that makes use of all available QOL data at each study assessment point to model the time profile (fixed effect). Using the fitted model, we can

estimate the overall difference in the QOL measures as well as test the global hypothesis of no difference over time. We can also estimate the difference in the areas under the two QOL treatment curves (and test the hypothesis of no difference, on average). In addition, we can estimate differences in QOL at the end of the study or at intermediate points. Lastly, to address the possibility that international differences in QOL exist despite our use of extensively culturally validated instruments, we will examine interactions between key QOL outcomes, treatment, and geographic region.

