1. LVEF <35%
2. History of unprotected left main stenosis \geq 50% on prior coronary computed tomography angiography (CCTA) or prior cardiac catheterization (if available)
3. Finding of "no obstructive CAD" (<50% stenosis in all major epicardial vessels) on prior CCTA or prior catheterization, performed within 12 months
4. Coronary anatomy unsuitable for either PCI or CABG
5. Unacceptable level of angina despite maximal medical therapy
6. Very dissatisfied with medical management of angina
7. History of noncompliance with medical therapy
8. Acute coronary syndrome within the previous 2 months
9. PCI within the previous 12 months
10. Stroke within the previous 6 months or spontaneous intracranial hemorrhage at any time

11. History of ventricular tachycardia requiring therapy for termination, or symptomatic sustained ventricular tachycardia not due to a transient reversible cause
12. NYHA class III-IV heart failure at entry or hospitalization for exacerbation of chronic heart failure within the previous 6 months
13. Non-ischemic dilated or hypertrophic cardiomyopathy
14. Severe valvular disease or valvular disease likely to require surgery or percutaneous valve replacement during the trial
15. Allergy to radiographic contrast that cannot be adequately pre-medicated, or any prior anaphylaxis to radiographic contrast
16. Planned major surgery necessitating interruption of dual antiplatelet therapy (note that patients may be eligible after planned surgery)
17. Life expectancy less than the duration of the trial due to non-cardiovascular comorbidity
18. Pregnancy (known to be pregnant; to be confirmed pre- randomization, if applicable)
19. Patient who, in the judgment of the patient's physician, is likely to have significant unprotected left main stenosis
20. Enrolled in a competing trial that involves a non-approved cardiac drug or device
21. Inability to comply with the protocol
22. Exceeds the weight or size limit for cardiac catheterization at the site
23. Canadian Cardiovascular Society Class III angina of recent onset, or angina of any class with a rapidly progressive or accelerating pattern
24. Canadian Cardiovascular Society Class IV angina, including unprovoked rest angina
25. High risk of bleeding which would contraindicate the use of dual antiplatelet therapy
26. Cardiac transplant recipient

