- For enrolled participants ischemia tests will be transferred electronically to the appropriate core laboratory. (see [section 5.4](#))

Randomization visit (Baseline Visit) (targeted within 15 days of participant’s consent)

- Medical history including CV medications will be documented
- NYHA and CCS class (see MOO)
- Brief symptoms/QOL assessment will be collected (prior to actual randomization)
- Modified Morisky medication adherence survey (see MOO)
- Vital signs, height and weight will be measured
- 12 lead ECG will be performed and sent to ECG core lab; stress ECG, and symptom, and hemodynamic results will be sent to ECG core lab
- Results of routine laboratory tests performed within 6 months of visit will be recorded, including HbA1c for diabetic participants. If these test results are not available a blood draw for routine laboratory tests will be done at this visit (see MOO)
- Baseline blood draw for biomarker/genetics biorepositories

- Eligible participants will be randomized to INV or CON strategies via the IVRS/IXRS system. (These participants are considered randomized)
- Participants randomized to INV strategy should target to undergo catheterization, with optimal revascularization to be completed within a target of 30 days from randomization
- PACE will be implemented for all participants
- Initiate OMT in all randomized participants according to guideline recommendations and study algorithms

Cath and Revascularization for participants randomized to INV strategy (protocol assigned); also applies to all revascularization procedures for participants in both management strategies

- For protocol assigned cardiac cath and revascularization (INV strategy participants), target completion within 30 days of randomization
- Revascularization to be performed as per Optimal Revascularization Therapy (ORT) (refer to MOO)
- For participants undergoing PCI
 - 12 lead ECG to be performed post-PCI at 60 ± 30 minutes, and as needed for chest pain
 - Blood draw for both CK-MB and troponin before PCI, and at 8-16 ± 2 hours post-PCI or at hospital discharge, whichever comes earlier, whenever possible
 - All pre- and post-procedure biomarker measurements that are obtained should be recorded on eCRF
- For participants undergoing CABG
 - 12 lead ECG to be performed on day 3 post-CABG or at hospital discharge whichever comes earlier, and as needed for chest pain

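### Section 11.2.4 does not name the pre-randomization SAQ score as a covariate or effect modifier, which costs precision and leaves no planned estimate by baseline angina

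*Combined protocol and SAP*

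**What the plan says.** - **Analysis.** The first stage in section 11.2.4 is "First, we will provide simple descriptive and comparative analyses by intention-to-treat". The second looks at change from baseline and uses regression to find what determines it. A mixed model of the time profile follows. The only treatment interaction named is regional: "we will examine interactions between key QOL outcomes, treatment, and geographic region".
- **Power.** The same section says its estimates "show that we should have in excess of 99% power to detect" one-quarter "SD differences in our 3 principal QOL measures". They rest on data from an earlier strategy trial (COURAGE). The inputs are not shown.
- **Entry.** Section 4.3.1 requires ischemia on a test and asks for no angina. The exclusions act at the severe or unstable end: "Unacceptable level of angina despite maximal medical therapy" (exclusion 5), "Very dissatisfied with medical management of angina" (exclusion 6), and recent-onset CCS class III, accelerating or class IV angina (23 and 24).
- **Baseline data.** For the randomization visit, section 9 says "Brief symptoms/QOL assessment will be collected (prior to actual randomization". Footnote N to Table 2 shows that this assessment includes SAQ items.
- **Elsewhere.** Section 11.2.1 provides for covariate adjustment and for effect modification, but for the primary endpoint, and the latter only if an overall difference is seen. Section 11.2.2 applies a similar analysis to the other secondary endpoints and refers quality of life to 11.2.4.

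**The concern.** The strongest predictor of a follow-up SAQ score is likely to be the same score before randomization. The plan collects it but does not say that it enters any between-arm comparison. A simple comparison ignores it, and a raw change score uses it inefficiently.

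Entry also leaves the symptom-free end of the scale open. A participant with no angina at entry can only stay the same or worsen on Angina Frequency. If such participants gain little from the invasive strategy, the overall mean difference is smaller than the difference among those with symptoms, and the plan produces no estimate for the latter. If that estimate is added only after results are known, it will be post hoc, for a patient-reported outcome in an unblinded trial.

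**Working it through.** **Inputs from the documents:** "500 participants per group" (section 11.1.1), two-sided tests (11.2), and a 1/4 SD difference with power above 99% (11.2.4).

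**Assumed, because the documents do not give them:** alpha 0.05 for quality of life (it is stated for the primary endpoint); the baseline to follow-up correlation r; the share f with angina at entry; the benefit d in that share, in SD units; zero benefit in the rest; a common SD; complete SAQ data.

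**1. The plan's own figure.** The standard error of a difference in means is √(2/500) = 0.0632 SD. Then 0.25/0.0632 − 1.96 = 3.953 − 1.960 = 1.993, which gives power 97.7%. That is close to the stated figure but not above 99%. Without adjustment, 99% needs 588 per arm. With baseline adjustment, 500 per arm reaches 99% from r of about 0.39. The documents do not say which calculation was done. Either way, the figure takes the shift as an average over everyone.

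**2. Precision.** With variance σ² at both times, the variance per participant is:
- follow-up score alone: σ²
- change score: 2(1 − r)σ²
- follow-up adjusted for baseline: (1 − r²)σ²

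The sample-size value of adjustment is 1/(1 − r²) against follow-up alone. Against change it is 2(1 − r)/(1 − r²) = 2/(1 + r).

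| r | against follow-up alone | against change score |
|---|---|---|
| 0.4 | 1.19 | 1.43 |
| 0.5 | 1.33 | 1.33 |
| 0.6 | 1.56 | 1.25 |

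The gain is therefore 19 to 56% against the first and 43 to 25% against the second, moving in opposite directions as r rises.

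**3. Dilution.** The pooled effect is f × d. Pooled power uses f × d with 500 per arm. Power in the symptomatic stratum uses d with 500f per arm. The standard error of the treatment-by-baseline-angina interaction is √[2/(500f) + 2/(500(1 − f))].

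| d (SD) | f | pooled effect (SD) | pooled power | symptomatic stratum | interaction |
|---|---|---|---|---|---|
| 0.25 | 0.75 | 0.1875 | 84% | 93% | 40% |
| 0.25 | 0.50 | 0.125 | 51% | 80% | 51% |
| 0.25 | 0.30 | 0.075 | 22% | 58% | 44% |
| 0.50 | 0.75 | 0.375 | >99.9% | >99.9% | 93% |
| 0.50 | 0.50 | 0.25 | 98% | >99.9% | 98% |
| 0.50 | 0.30 | 0.15 | 66% | 99% | 95% |

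Worked case, d = 0.25 and f = 0.5:
- pooled: 0.125/0.0632 − 1.96 = 0.016, or 51%
- symptomatic half: 0.25/√(2/250) − 1.96 = 2.795 − 1.960 = 0.835, or 80%

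**4. Both together.** With baseline adjustment at r = 0.5, taken as equal in the whole sample and the subset, the worked case rises from 51% to 63% pooled and from 80% to 90% in the symptomatic half.

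**The case against.** A reader might infer that pooling makes the plan answer its secondary objective wrongly. The documents do not support that. The synopsis and section 3 set the SAQ objective for trial participants as a whole, and the intention-to-treat mean is an unbiased answer to it. A reader might also infer that regression to the mean distorts the change scores. It acts on both randomized arms alike and does not bias the difference between them.

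Other points have force:
- The share without angina is unknown. The exclusions remove the severe or unstable end, while stable class I–II and class III angina not of recent onset remain eligible.
- Zero benefit in symptom-free participants is an assumption. The invasive strategy could prevent angina from developing over about 4 years, and that counts as angina control.
- With a 0.50 SD benefit and half symptomatic, pooled power is about 98%, so a missed effect is a possibility and not a demonstrated consequence.
- The mixed model may already take baseline as a response, in which case much of the precision gain is in hand.
- Section 11.2 defers detail to a later analysis plan, and the regression on determinants of change could include the baseline score.
- Section 11.2.4 deliberately limits the number of formal comparisons.

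These points narrow the concern but do not remove it. The text does not say how baseline enters the mixed model. A search for determinants of change does not show how the treatment difference varies with starting angina. Section 11.2.1 assigns covariates and subgroups for the primary endpoint to the later plan, whereas 11.2.4 assigns nothing comparable for SAQ. The multiplicity point is met by giving the added estimates descriptive status.

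**Conclusion.** The concern holds as one of precision and missing information, not of validity. Section 11.2.4 leaves out a covariate that is already collected. The loss is equivalent to 19 to 56% more participants against an unadjusted follow-up score, or 43 to 25% against a change score, for r from 0.4 to 0.6 with equal variances. It is less where the mixed model already uses baseline as a response.

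The dilution is conditional. It depends on f, on d and on little or no benefit in symptom-free participants, none of which the documents give. Over the values shown, pooled power runs from 22% to above 99.9%. What does not depend on those values is that no estimate by baseline angina is planned, so a small overall difference could not be interpreted for participants with symptoms.

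**What to change.** Keep the overall intention-to-treat comparison, and add two items to section 11.2.4 or to the later analysis plan before any unblinded analysis:

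1. Include the pre-randomization score of the same SAQ scale as a covariate in every between-arm SAQ comparison, in place of raw change from baseline. Do the same in the mixed model unless baseline is modelled there as a response, and state which (for example, with one baseline mean common to both arms).
2. Pre-specify the INV–CON difference by baseline SAQ Angina Frequency level, with descriptive status, to be reported whatever the overall result.

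The cost is wording only: no new data, visits or participants. Intervals within the symptomatic subset will be wider than for the full sample. The interaction has limited power (about 51% at 0.25 SD with half symptomatic), so the estimates and their intervals should be read rather than the interaction test.
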